6.4.3 Day 7 (Visit 5) ± 2 Days

The following procedures will be performed at Visit 5:

- Record weight;
- Perform 12-lead ECG in triplicate (patients should be resting in a supine position for at least 10 minutes prior to assessment);
- Obtain vital signs, including pulse rate, respiratory rate, and oral temperature;
- Obtain blood pressure prior to study drug administration;
 - Blood pressures are to be obtained according to the AHA recommendations for accurate blood pressure measurement. Patients should avoid smoking, caffeine, or exercise within 30 minutes before measurement; empty his or her bladder; then sit quietly in a comfortable

chair with back support for at least 10 minutes before measurement and remain still during the measurement. The patient's limb should be supported to measure blood pressure to ensure that the blood pressure cuff is at heart level, using the correct cuff size. Do not take the measurement over clothes. Blood pressure measurements should be performed in the same arm throughout the study. Triplicate blood pressure measurements should be taken approximately 2 minutes apart with a validated, oscillometric upper arm blood pressure monitor. Trough cuff SBP and DBP values will be assessed based on the pre-defined blood pressure measurement guideline throughout the study. Pulse will be obtained simultaneously with blood pressure measurements;

- Obtain blood sample for clinical laboratory tests (central laboratory; see Appendix B);
- Obtain urine sample for:
 - o Urinalysis (central laboratory; see Appendix B); and
 - o UACR;
- Obtain serum sample for potassium (local and central laboratories);
- Obtain serum sample for creatinine (central laboratory);
- Record adverse events and concomitant medications;
- Check study drug accountability and collect unused study drug;
- Administer daily dose of study drug and record time; and
- Instruct patient on study drug and re-dispense study drug.

6.4.4 Day 14 (Visit 6) ± 2 Days

The following procedures will be performed at Visit 6:

- Record weight;
- Obtain vital signs including pulse rate, respiratory rate, and oral temperature;
- Obtain blood pressure prior to study drug administration;
 - O Blood pressures are to be obtained according to the AHA recommendations for accurate blood pressure measurement. Patients should avoid smoking, caffeine, or exercise within 30 minutes before measurement; empty his or her bladder; then sit quietly in a comfortable chair with back support for at least 10 minutes before measurement and remain still during the measurement. The patient's limb should be supported to measure blood pressure to ensure that the blood pressure cuff is at heart level, using the correct cuff size. Do not take the measurement over clothes. Blood pressure measurements should be performed in the same arm throughout the study. Triplicate blood pressure measurements should be taken approximately 2 minutes apart with a validated, oscillometric upper arm blood pressure monitor. Trough cuff SBP and DBP values will be assessed based on the pre-defined blood pressure measurement guideline throughout the study. Pulse will be obtained simultaneously with blood pressure measurements;
- Obtain blood sample for clinical laboratory tests (central laboratory; see Appendix B);

- Obtain urine sample for:
 - o Urinalysis (central laboratory; see Appendix B); and
 - o UACR;
- Obtain serum sample for potassium (local and central laboratories);
- Obtain serum sample for creatinine (central laboratory);
- Obtain plasma sample for PK from all patients (pre-dose). If patients are not dosed in the unit on this day, a PK sample will be collected, and the date and time of the last dose will be recorded;
- Record adverse events and concomitant medications;
- Check study drug accountability and collect unused study drug;
- Administer daily dose of study drug and record time; and
- Instruct patient on study drug and re-dispense study drug.

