Plasma samples for PK analysis will be collected from all patients. A total of 4 PK samples will be collected from each patient, including at Day 1 (prior to discharge), Day 14 pre-dose, Day 28 pre-dose, and the End of Study Visit (Day 112)/Early Termination Visit. The pre-dose samples assume that patients will be dosed in the unit on the days above. If patients are not dosed in the

unit on those days, a PK sample will be collected during each of these visits and the date and time of the last dose will be recorded.

Safety will be assessed systematically, and an independent data monitoring committee will perform cumulative reviews of safety data at regular intervals during the study.

Serum potassium levels, serum creatinine, and blood pressure will be monitored throughout the study and clinically significant changes will be reported as adverse events of special interest.

At Screening and the end of the placebo run-in period (Visit 3), patients must have uncontrolled hypertension (Grade 1 to 2 systolic hypertension – ESC/ESH), defined as resting trough-cuff seated SBP \geq 140 and \leq 179 mmHg, based on the mean of at least 2 current consecutive blood pressure readings in the clinic, a serum potassium \leq 4.8 mmol/L at Screening and the end of the placebo run-in period (Visit 3), and a mean (Visit 1 and Visit 3) eGFR \geq 15 and \leq 44 mL/min/1.73 m².

In all cases, dose and frequency of concurrent antihypertensive medications are expected to be maintained without dose adjustment for 30 days prior to randomization in order to ensure that blood pressure is stable. In general, patients should not add or adjust dose and/or types of the antihypertensive medications they are receiving during the screening period and throughout the duration of the study (unless they develop symptomatic hypotension). The dose of diuretic may be adjusted based on developing or resolved edema, weight gain or loss, or pulmonary congestion.

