9.2.4 Analysis of Pharmacokinetics

The analysis of the PK/PD relationship will be explored. Population PK models will be built using a nonlinear mixed effects modeling technique with NONMEM software based on the PPK Population. Different PK models will be attempted to fit the PK concentration-time data. After the PPK modeling, a population PD approach will be used to explore the concentration-effect relationships. Different PD models will be attempted to fit the concentration-effect data. All PD exploration will be based on the ITT Population.

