- 12. Blood pressure and heart rate measurements will be obtained every 20 minutes during the interval of 06:00:00 hours to 21:59:59 hours (to coincide with the daytime, awake period), and every 30 minutes during the interval of 22:00:00 hours to 05:59:59 hours (to coincide with the nighttime, sleeping period). During the 24-hour ABPM recording period, a diary will be provided to the patient. Instructions and training will be provided to the site staff, who will in turn provide instructions to the patient.
- 13. If a patient has completed the 24-hour ABPM recording since their last visit, 24-hour ABPM data will be downloaded at the site during the ET Visit.
- 14. Clinical laboratories include chemistry, hematology, coagulation, and urinalysis. See Appendix B for the complete list of clinical laboratory analytes assessed for this study.
- 15. Only clinical chemistry will be conducted at the end of run-in period (Visit 3).
- 16. All patients must have a serum potassium ≤ 4.8 mmol/L at both Screening and the end of the placebo run-in period (Visit 3).
- 17. Serum pregnancy tests will be obtained at Screening, EOS, and ET. A urine pregnancy test will be obtained at pre-dose on Day 1.

- 18. Post-menopausal women only.
- 19. Serum/plasma samples taken during the study will be stored at a central laboratory for determination of various additional biomarkers, including but not limited to galectin-3, N-terminal of the prohormone brain natriuretic peptide, interleukin-6, collagen biomarkers, and C-reactive protein. The panel of biomarkers and time points for analysis will be determined prior to the database lock.
- 20. Plasma samples are to be collected prior to patient's discharge from the unit.
- 21. Plasma samples are to be collected pre-dose. If patients are not dosed in the unit on those days, a PK sample will be collected, and the date and time of the last dose will be recorded.
- 22. Open-label placebo will be dispensed at Visit 2.
- 23. The first dose of the study drug is to be administered.
- 24. The daily dose of the study drug is to be administered.
- 25. If a patient's compliance to medications (including both open-label placebo and current antihypertensive medications) is < 80% or > 120% at Visit 3, he/she will not be eligible for the study and no further visits will be performed.

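### For patients dosed in the unit on Days 14 and 28, the protocol does not ask for the time of the home dose that precedes the pre-dose PK sample

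*Combined protocol and SAP*

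**What the plan says.** Section 6.4.4 (Day 14) calls for a pre-dose PK sample from all patients. It then adds a condition: "If patients are not dosed in the unit on this day, a PK sample will be collected, and the date and time" of the most recent dose are to be noted. Later in the same visit list comes "Administer daily dose of study drug and record time". Section 6.4.5 (Day 28) has the same two items. Footnote 21 of Appendix A repeats the condition: "Plasma samples are to be collected pre-dose. If patients are not dosed in the unit on those days, a PK sample will be collected", again with the last-dose time attached only to that case.

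The synopsis and Section 3.1 state which case is expected: "The pre-dose samples assume that patients will be dosed in the unit on the days above". They list four samples per patient: Day 1 before discharge, Day 14 pre-dose, Day 28 pre-dose, and Day 112 or early termination.

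Section 9.2.4 describes the use of the data: nonlinear mixed effects models, where "Different PK models will be attempted to fit the PK concentration-time data". Section 2.2 lists population PK as a secondary objective.

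**The concern.** A pre-dose concentration depends on the doses taken before it, above all the most recent one. For a patient dosed in the unit, that is a home dose, usually taken the day before. The protocol does not ask when it was taken. It asks for the time of the visit dose, which follows the sample and cannot influence it. Patients not dosed in the unit do have the relevant time recorded, so the condition omits it in the case the design expects.

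At stake is the quality of the population PK analysis. If the interval since the last dose is wrong or filled in with a nominal value, variation in dose timing appears as residual error or as differences between patients in clearance. Section 5.2 cites exposure up to around 60% higher in severe CKD and a possible link between exposure and hyperkalemia as part of the dose rationale. Added timing error would make relations of that kind harder to see in this trial's data.

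**Working it through.** The plan states no figure on this point, so there is none to reproduce. The check has two parts.

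**1. Which dose time is required for each patient**

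| Patient on Day 14 or 28 | Time of dose before the sample | Time of dose after the sample |
|---|---|---|
| Dosed in the unit (default: synopsis, 3.1) | Not required | Required (6.4.4, 6.4.5) |
| Not dosed in the unit | Required (6.4.4, 6.4.5, footnote 21) | Not applicable |

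Other places where the missing time might be captured:

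- Section 5.5.3 says once daily and sets no clock time.
- Section 5.5.4 relies on tablet counts, and on questioning if necessary. A count gives the number of doses taken, not their clock times or which day was missed.
- The only diary (6.4.1, 6.4.6, 6.4.9, 7.2) belongs to the ABPM recording.
- The in-unit dose time at Day 7 (6.4.3) is about a week before the Day 14 sample, and the one at Day 14 is two weeks before the Day 28 sample.

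None supplies the time. Of the four samples, Day 1 falls on the day of first dosing and Day 112 about four weeks after treatment ends. Days 14 and 28 are therefore the only two scheduled during repeated dosing. With 80 patients in each of two active groups, that is up to 2 × 160 = 320 concentrations before dropout.

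**2. How much an unrecorded deviation could matter**

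Assumptions, none taken from the documents: half-life T of 24, 48 or 72 h; mono-exponential decline; accumulation complete; nominal interval 24 h. Write r = 2^(−24/T).

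- Nominal trough is proportional to r + r² + … = r/(1 − r). The last dose contributes r of this, a share of 1 − r.
- One dose 4 h late changes the trough by (1 − r)(2^(4/T) − 1). One dose 4 h early changes it by (1 − r)(2^(−4/T) − 1).
- If every home dose is offset by 4 h from the sample time, the whole trough is multiplied by 2^(±4/T).
- If the previous day's dose is missed, the trough becomes r² + r³ + …, which is r times nominal.

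| T | r | Last-dose share | One dose 4 h late / early | All doses offset 4 h | Dose missed the day before |
|---|---|---|---|---|---|
| 24 h | 0.500 | 50% | +6.1% / −5.5% | +12% / −11% | −50% |
| 48 h | 0.707 | 29% | +1.7% / −1.6% | +6% / −6% | −29% |
| 72 h | 0.794 | 21% | +0.8% / −0.8% | +4% / −4% | −21% |

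Worked line for T = 24 h: 0.5 × (2^(4/24) − 1) = 0.5 × 0.122 = 6.1%. For T = 72 h: 0.206 × (2^(4/72) − 1) = 0.206 × 0.039 = 0.8%.

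**The case against.** The strongest reply is that the consequences are limited. Population PK is the last-listed secondary objective, and Section 9.2.4 describes the PK/PD work as exploratory. Neither the SBP analysis nor the incidence of hyperkalemia uses these concentrations. Dosing is once daily, so a nominal interval of about 24 h is available. Tablet counts give some warning of missed doses. The eCRF is not among the documents, and Section 8.7 leaves sampling details to a laboratory manual, so the time may be collected anyway. All of this stands, and it limits the size of the point. It does not supply the time in the protocol, which asks for it in one case and leaves it out in the expected one.

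A reader might also infer more than the documents support:

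- **That the interval is unknown, or that the model must take exactly 24 h for everyone.** The supported statement is that recording is not required. Section 9.2.4 prescribes no 24 h assumption, and patients not dosed in the unit have the time recorded.
- **That these are steady-state samples.** No section calls them that. Complete accumulation is an assumption of the arithmetic here.
- **That a single home dose 4 h off moves the trough by 4% to 12%.** That range needs every home dose to be offset. One dose alone gives about 1% to 6%.
- **That Day 112 and early termination have the same gap.** The rule in the synopsis and Section 3.1 covers all four sampling visits. No dose is given at these two, so the last-dose time is already required. Sections 6.5 and 6.6 merely do not repeat it.
- **That the last two dose times are needed.** The last dose before the sample closes the gap. Its date alone shows a dose missed the day before.

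**Conclusion.** The point holds for Days 14 and 28. On the path the design assumes, the protocol requires the time of a dose that cannot affect the sample and not the time of the one that does. Lost home-dose times are hard to recover later.

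The effect on any one concentration runs from about 1% (one dose 4 h off, 72 h half-life) to about 50% (a missed dose, 24 h half-life). It rests on an assumed half-life of 24 to 72 h; a longer half-life would make every figure smaller. The documents give no rate of late or missed doses, so the total effect on the PK model cannot be stated. The damage is added error in a secondary analysis. The correction is worth making because it is cheap and cannot be made after the visits have passed.

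**What to change.** Remove the condition in Sections 6.4.4 and 6.4.5, the synopsis, Section 3.1 and Appendix A footnote 21. Suggested wording: at the Day 14 and Day 28 PK samples, record for every patient, whether or not dosed in the unit, the time of the sample and the date and time of the last dose of study drug taken before it. Keep the existing record of the visit dose time.

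No change of substance is needed for Day 112 or early termination; a cross-reference in Sections 6.5 and 6.6 to the rule in Section 3.1 would be a convenience only.

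The cost is one eCRF entry and one question to the patient at visits already held. The drawback is reliance on recall, which the protocol already accepts for patients not dosed in the unit. No dose, schedule or clinical rule changes.

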6.4.5 Day 28 (Visit 7) ± 3 Days

The following procedures will be performed at Visit 7:

- Record weight;
- Contact IRT;
- Obtain vital signs including pulse rate, respiratory rate, and oral temperature;
- Obtain blood pressure prior to study drug administration;
 - Blood pressures are to be obtained according to the AHA recommendations for accurate blood pressure measurement. Patients should avoid smoking, caffeine, or exercise within 30 minutes before measurement; empty his or her bladder; then sit quietly in a comfortable chair with back support for at least 10 minutes before measurement and remain still during the measurement. The patient's limb should be supported to measure blood pressure to ensure that the blood pressure cuff is at heart level, using the correct cuff size. Do not take the measurement over clothes. Blood pressure measurements should be performed in the same arm throughout the study. Triplicate blood pressure measurements should be taken approximately 2 minutes apart with a validated, oscillometric upper arm blood pressure monitor. Trough cuff SBP and DBP values will be assessed based on the pre-defined blood pressure measurement guideline throughout the study. Pulse will be obtained simultaneously with blood pressure measurements;
- Obtain blood sample for clinical laboratory tests (central laboratory; see Appendix B);
- Obtain urine sample for:
 - o Urinalysis (central laboratory; see Appendix B); and
 - o UACR;
- Obtain serum sample for potassium (local and central laboratories);

- Obtain serum sample for creatinine (central laboratory);
- Obtain plasma sample for PK from all patients (pre-dose). If patients are not dosed in the unit on this day, a PK sample will be collected, and the date and time of the last dose will be recorded;
- Record adverse events and concomitant medications;
- Check study drug accountability and collect unused study drug;
- Instruct patient on study drug and re-dispense study drug;
- Administer daily dose of study drug and record time; and
- Instruct patient on 24-hour urine collection to be provided at Visit 8 and dispense laboratory materials for collection.

6.4.6 Day 40 (ABPM Visit) ± 3 Days

This visit is for 24-hour ABPM patients only (a subset of up to 40 patients per treatment group who agree to participate in 24-hour ABPM and still meet eligibility criteria at the end of the run-in period [Visit 3]).

The following procedure will be performed at the ABPM Visit:

• 24-hour ABPM device placement and start. Blood pressure and HR measurements will be obtained every 20 minutes during the interval of 06:00:00 hours to 21:59:59 hours (to coincide with the daytime, awake period) and every 30 minutes during the interval of 22:00:00 hours to 05:59:59 hours (to coincide with the nighttime, sleeping period). During the 24-hour ABPM recording period, a diary will be provided to the patient. Instructions and training will be provided to the site staff, who will in turn provide instructions to the patient.

6.4.7 Day 42 (Visit 8) ± 3 Days

The following procedures will be performed at Visit 8:

- Record weight;
- Obtain vital signs including pulse rate, respiratory rate, and oral temperature;
- Obtain blood pressure prior to study drug administration;
 - O Blood pressures are to be obtained according to the AHA recommendations for accurate blood pressure measurement. Patients should avoid smoking, caffeine, or exercise within 30 minutes before measurement; empty his or her bladder; then sit quietly in a comfortable chair with back support for at least 10 minutes before measurement and remain still during the measurement. The patient's limb should be supported to measure blood pressure to ensure that the blood pressure cuff is at heart level, using the correct cuff size. Do not take the measurement over clothes. Blood pressure measurements should be performed in the same arm throughout the study. Triplicate blood pressure measurements should be taken approximately 2 minutes apart with a validated, oscillometric upper arm blood pressure monitor. Trough cuff SBP and DBP values will be assessed based on the pre-defined blood pressure measurement guideline throughout the study. Pulse will be obtained simultaneously with blood pressure measurements;

- Obtain blood sample for clinical laboratory tests (central laboratory; see Appendix B);
- Obtain urine sample for:
 - Urinalysis (central laboratory; see Appendix B);
 - o UACR; and
 - o 24-hour urine for UACR;
- Obtain serum sample for potassium (local and central laboratories);
- Obtain serum sample for creatinine (central laboratory);
- Record adverse events and concomitant medications;
- Check study drug accountability and collect unused study drug;
- Instruct patient on study drug and re-dispense study drug;
- Administer daily dose of study drug and record time; and
- Download 24-hour ABPM readings at site (for a subset of up to 40 patients per treatment group who agree to participate in 24-hour ABPM and still meet eligibility criteria at the end of the run-in period [Visit 3] who undergo 24-hour ABPM).

6.4.8 Day 56 (Visit 9) ± 3 Days

The following procedures will be performed at Visit 9:

- Record weight;
- Contact IRT;
- Obtain vital signs including pulse rate, respiratory rate, and oral temperature;
- Obtain blood pressure prior to study drug administration;
 - O Blood pressures are to be obtained according to the AHA recommendations for accurate blood pressure measurement. Patients should avoid smoking, caffeine, or exercise within 30 minutes before measurement; empty his or her bladder; then sit quietly in a comfortable chair with back support for at least 10 minutes before measurement and remain still during the measurement. The patient's limb should be supported to measure blood pressure to ensure that the blood pressure cuff is at heart level, using the correct cuff size. Do not take the measurement over clothes. Blood pressure measurements should be performed in the same arm throughout the study. Triplicate blood pressure measurements should be taken approximately 2 minutes apart with a validated, oscillometric upper arm blood pressure monitor. Trough cuff SBP and DBP values will be assessed based on the pre-defined blood pressure measurement guideline throughout the study. Pulse will be obtained simultaneously with blood pressure measurements;
- Obtain blood sample for clinical laboratory tests (central laboratory; see Appendix B);

- Obtain urine sample for:
 - o Urinalysis (central laboratory; see Appendix B); and
 - o UACR;
- Obtain serum sample for potassium (local and central laboratories);
- Obtain serum sample for creatinine (central laboratory);
- Record adverse events and concomitant medications;
- Check study drug accountability and collect unused study drug;
- Instruct patient on study drug and re-dispense study drug;
- Administer daily dose of study drug and record time; and
- Instruct patient on 24-hour urine collection to be provided at Visit 10 and dispense laboratory materials for collection

6.4.9 Day 82 (ABPM Visit) ± 3 Days

This visit is for 24-hour ABPM patients only (a subset of up to 40 patients per treatment group who agree to participate in 24-hour ABPM and still meet eligibility criteria at the end of the run-in period [Visit 3]).

The following procedure will be performed at the ABPM Visit:

• 24-hour ABPM device placement and start. Blood pressure and HR measurements will be obtained every 20 minutes during the interval of 06:00:00 hours to 21:59:59 hours (to coincide with the daytime, awake period), and every 30 minutes during the interval of 22:00:00 hours to 05:59:59 hours (to coincide with the nighttime, sleeping period). During the 24-hour ABPM recording period, a diary will be provided to the patient. Instructions and training will be provided to the site staff, who will in turn provide instructions to the patient.

